**REVISION HISTORY**

Revision #	Version Date	Summary of Changes	Consent Change?
1	12/1/2023	1. Changed title to Effects of high-intensity muscle training as a pre-cardiac rehabilitation intervention on cardiovascular function in patients with heart disease  2. Expand participant population to include those with a history of percutaneous coronary interventions, heart failure, and/or myocardial infarction.	Yes  Yes

## 1.0 Study Summary

**Background / aim:** Endothelial function is closely associated with coronary artery health among individuals being treated for heart disease. An impairment in endothelial function promotes arterial stiffening that directly contributes to elevated systolic blood pressure as a result of increased vascular resistance. Inspiratory muscle training is simply a form of training consisting of repeated inspirations against a resistance. Inspiratory muscle training has also been applied to patients with chronic disease or as an additional therapy for cardiac rehabilitation and it has proven to be safe in these groups. Few studies in the literature examined the effects of high intensity inspiratory muscle training in this population, however, these studies did not examine the direct effects of inspiratory muscle training on vascular function. To the best of our knowledge, the effects of inspiratory muscle training in patients with heart disease on endothelial function and arterial stiffness prior to starting cardiac rehabilitation have not been investigated.

**Methods:** The study was designed as a randomized controlled trial. The demographic and clinical characteristics of the patients will be recorded after consent is obtained from the volunteer patients who meet the inclusion criteria. Subsequently, patients will be randomly divided into two groups (22 subjects in each group) for inspiratory muscle training (IMT) with 60% of maximum inspiratory pressure (MIP) or sham inspiratory muscle training (Sham-control), for 4 weeks. In both groups, before and after 4-week-training, resting blood pressure (systolic/diastolic), resting heart rate, endothelial function, arterial stiffness, functional exercise capacity, the severity of dyspnea and inspiratory muscle functions will be measured.

## 2.0 Objectives\*

**2.1 Objectives:** The aim of this study is to investigate and interpret whether high-intensity inspiratory muscle training, beyond the usual care of heart disease, improves endothelial function and arterial stiffness.

**2.2 Hypotheses:** High-intensity inspiratory muscle training will improve endothelial function and arterial stiffness beyond the usual care of patients with heart disease.

## 3.0 Background\*

Cardiovascular diseases (CVD) remains a leading cause of morbidity and mortality in both men and women in developed and developing societies (Joseph et al., 2017). Some degree of pulmonary dysfunction is highly likely in patients with heart disease compared to those without(Calles et al., 2016; Cahalin and Arena, 2015). This can affect pulmonary function, gas exchange, as well as decrease maximum inspiratory and expiratory pressures (MIP and MEP, respectively)(Dos Santos et al., 2019; Haeffner et al., 2008; Roncada et al., 2015; Cahalin and Arena, 2015).

**PROTOCOL TITLE:** Effects of high-intensity inspiratory muscle training as a pre-cardiac rehabilitation intervention on cardiovascular functions in patients with heart disease

Inspiratory muscle training has been shown to be an effective form of training that enhances lung function. It consists of repetitive breath cycles where one inspires against resistance placed by a device and expires against no resistance. Studies that have applied this form of training in patients with heart disease have found significant improvements in MIP-MEP, tidal volume, vital capacity, and 6-minute walking distance. Few studies have examined the effects of high-intensity (between 50-80% of MIP) inspiratory muscle training in patients with heart disease (Dos Santos et al., 2019; Dos Santos et al., 2021; Laoutaris et al., 2007; Miozzo et al., 2018; Sadek et al., 2022). This level of training has been associated with greater improvements in the aforementioned outcomes of interest, however, no study has explored the effects of high-intensity inspiratory muscle training in patients with heart disease on measures of cardiovascular function.

This study will therefore examine the effects of high-intensity inspiratory muscle training in patients with heart disease on cardiovascular function.

#### **4.0 Study Endpoints\***

- 4.1** Primary endpoints; inspiratory muscle function, endothelial function, arterial stiffness.
- 4.2** Secondary endpoints; dyspnea, functional exercise capacity.

#### **5.0 Study Intervention/Investigational Agent**

**5.1 Description of the study intervention:** Based on the findings of a systematic review (Z. Sadek et al., 2018), it has been determined that to achieve significant improvements in inspiratory muscle strength, the threshold pressure for inspiratory muscle training (IMT) should be set at 60% of the maximal inspiratory mouth pressure (MIP). Consequently, the intervention protocol for IMT involves using a threshold-loaded IMT device (Threshold IMT Philips® Resironics, Inc). In the IMT group, the initial intensity of the inspiratory threshold will be set at 60% of each patient's initial maximal MIP, which is then readjusted after 2 weeks of training to maintain the 60% of MIP throughout the 4-week period. Rates of perceived inspiratory effort on a modified Borg scale will also be used to determine the highest tolerable load for each patient (at the 4-6 level of 10) (Borg, 1982; Wilson and Jones, 1989). Patients will perform IMT for 2 sets of 30 repetitions, with one-minute intervals between each set (McConnell, 2013; Z. Sadek et al., 2018). Throughout the training sessions, patients will be instructed to maintain diaphragmatic breathing. On the other hand, the Sham-control group will follow the same training program using the same device, but without any inspiratory load. Both groups will perform the training program twice a day, five days a week, for a total of 4 weeks, under the supervision of a physiotherapist (McConnell, 2013). The supervision will be conducted remotely through telerehabilitation, utilizing video calls to connect with the patients without requiring them to physically visit the healthcare facility. To familiarize the participants with the training procedure, both the IMT and Sham-control groups will undergo a session without any load on the

**PROTOCOL TITLE:** Effects of high-intensity inspiratory muscle training as a pre-cardiac rehabilitation intervention on cardiovascular functions in patients with heart disease

day of the baseline assessments. Throughout the study, all participants will visit the healthcare facility for baseline assessments, final assessments, and an additional brief assessment session at the end of the second week of training to measure MIP and readjust the loading value. The assessment to be made at the end of the 2nd week of the 4-week training seasons will only include the assessment of inspiratory muscle function described in 11.1.5.

**5.2 Device Handling:** The Threshold IMT Philips products will be obtained by researchers and provided to patients without any cost. The Threshold IMT Philips products is a legally marketed device when used in accordance with its labeling. There are no expected adverse events based on the product label. They will be used only on subjects and be used only by authorized investigators. On the other hand, a patient who loses the product before the study ends will be notified that he or she will be excluded from the study.

## **6.0 Study Timelines\***

- The duration of an individual subject's participation in the study will be 4 weeks.
- The duration anticipated to enroll all study subjects is 9 months.
- The estimated duration for the investigators to complete this study is 10 months.
- The estimated date for the investigators to complete this study is June 14, 2024.

## **7.0 Inclusion and Exclusion Criteria\***

### **7.1 Inclusion criteria as follows;**

- Aged >18 years old
- Be able to walk independently.
- Had coronary artery bypass graft (CABG) surgery, history of percutaneous coronary interventions, heart failure, and/or myocardial infarction.
- Sufficient English language comprehension and cognitive ability to understand the study protocol, give informed consent and follow instructions.

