### **7.2 Exclusion criteria as follows;**

- <18 years of age

**PROTOCOL TITLE:** Effects of high-intensity inspiratory muscle training as a pre-cardiac rehabilitation intervention on cardiovascular functions in patients with heart disease

- Being a current smoker (or tobacco).
- Having a diagnosed chronic disease such as inflammatory bowel disease/irritable bowel syndrome, cerebrovascular diseases, COPD, chronic kidney disease requiring dialysis, neurological disorders, or diseases that may affect motor/cognitive function [multiple sclerosis, Parkinson's disease, polio, Alzheimer's disease, dementia, or other brain diseases of ageing])
- Getting a score below 24 on the Standardized Mini Mental Test
- Using antipsychotic medications commonly used to treat schizophrenia or schizoaffective disorders (i.e., haloperidol)
- Having had any other previous thoracic operation except CABG (e.g. Pneumonectomy, lobectomy, etc.)
- Having a history of unstable-angina
- Having had pneumonia in the last 3 months

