## **10.0 Recruitment Methods**

**PROTOCOL TITLE:** Effects of high-intensity inspiratory muscle training as a pre-cardiac rehabilitation intervention on cardiovascular functions in patients with heart disease

For research purposes only, we propose to recruit patients that have undergone CABG surgery, history of percutaneous coronary interventions, heart failure, *and/or* myocardial infarction. Potential participants may be recruited at University of Illinois Health (UIH) clinics including Division of Cardiology ([name]). Potential participants may *actively* be recruited from the Outpatient UIH Heart Center, and the Cardiac Rehabilitation ([name]) and Exercise Testing ([name]) Programs via clinician referral during patient's routine visit.

Patients may be identified via clinician referral during routine in person visits or phone calls used to schedule a cardiac rehabilitation orientation visit. [name] and their staff may also notify [name] about whether and when any patients who meet the study criteria are scheduled to be seen in the clinic during the day or the following day. Patients that have received a referral to cardiac rehabilitation will be given the opportunity to take part in the study as long as the study requirements can be completed prior to their cardiac rehabilitation start date. Cardiac rehabilitation will not be delayed for the sole purpose of taking part in the study. Patients will not be able to do both study and cardiac rehabilitation at the same time as exercise is known to improve cardiovascular function.

The informed consent will be obtained from volunteer patients who meet the inclusion criteria. Patients will then be randomly assigned to a study or control group. The randomization sequence will generate from the [www.randomizer.org](http://www.randomizer.org) website by an investigator not otherwise involved in the study, using a table of random numbers uniformly distributed and divided into 2 groups. No names or personal identification will be given out.

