## **11.0 Procedures Involved\***

This research will take place in the Physical Therapy Faculty Practice located at [name] in Chicago, IL. It will be an interventional randomized controlled study. The data will be collected for research purposes only. We will ensure to participants that no new information (i.e., results from any study procedures) will be entered into or collected from patient's medical records. After eligibility is determined, those who agree to participate (provide oral consent) will be required to provide written informed consent statement before proceeding to subsequent data collection. All participants, both control and intervention, will be assessed with the following assessments.

Baseline Clinical Data collected will include demographics, level of educational attainment and past-medical history. Anthropometrics, Body Mass (kg) and height (m) will be assessed. (**visit #1**)

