- Encryption: All electronic data collected during the study will be encrypted to ensure its security during transmission and storage. Data will be transmitted securely using encrypted methods and stored on secure hard drives.
- Physical Controls: All physical documents and materials containing patient data will be stored in locked cabinets or rooms with access restricted to authorized personnel only.
- Separation of Identifiers and Data: Identifiers, such as names and, will be stored separately from study data to ensure the privacy and confidentiality of participants. Identifiers will only be used to link study data to the participants, and they will be removed once the data analysis is complete.

**PROTOCOL TITLE: Effects of high-intensity inspiratory muscle training as a pre-cardiac rehabilitation intervention on cardiovascular functions in patients with heart disease**

**17.3** The data will be handled study-wide as follows: All written data collection forms and electronic data will be handled and stored by principal investigator. The written data collection forms will be stored in PI's locked office in a locked filing cabinet. The research electronic data will be stored using the UIC Health Box Data Folder electronic database.

Authorized research personnel will maintain a master sheet which has the subject's name linked to their code. This sheet will be maintained within the UIC Health Box Data Folder designated for the study. All personal identifiable data will be destroyed 10 years after study completion. Results published will not include names of subjects. Some personal health information will be collected during the screening process, including name, contact information, and for individuals who meet the inclusion and exclusion criteria, dates of birth and CABG.

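### Eligibility now covers PCI, heart failure and MI with no time limit, but only the CABG date is named for collection and no analysis uses diagnosis or time since event: a precision and chance-imbalance gap, not a bias

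*Protocol*

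**What the plan says.** **Population.** The protocol's revision history, dated 12/1/2023, records the change: "Expand participant population to include those with a history of percutaneous coronary interventions, heart failure, and/or myocardial infarction". Section 7.1 now admits patients who "Had coronary artery bypass graft (CABG) surgery, history of percutaneous coronary interventions, heart failure, and/or myocardial infarction". No limit on time since the event is given. The only recency limit in section 7.2 concerns another illness: "Having had pneumonia in the last 3 months". Section 10 lets patients referred to cardiac rehabilitation take part "as long as the study requirements can be completed prior to their cardiac rehabilitation start date", which bounds when participation ends but not how long ago the event happened.

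**Dates and history.** Section 17.3 lists personal health information taken at screening, including, "for individuals who meet the inclusion and exclusion criteria, dates of birth and CABG". Section 11 adds: "Baseline Clinical Data collected will include demographics, level of educational attainment and past-medical history". The content of that history, and whether it carries dates, is not specified.

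**Allocation.** Section 1 says "patients will be randomly divided into two groups (22 subjects in each group"). Section 10 describes the list as produced "using a table of random numbers uniformly distributed and divided into 2 groups". No strata, blocks or minimisation are mentioned.

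**Analysis.** Section 17.1 of the protocol specifies ANCOVA with the outcome's baseline value as covariate. The SAP, dated 12/12/2023 and so later than Revision 1, specifies analysis of variance on mean change with no covariate. Neither uses the qualifying diagnosis or time since event.

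**The concern.** All endpoints are read over 4 weeks. Under section 7.1, a patient a few weeks past surgery and a patient whose PCI was years ago can both be randomised. If the first is still recovering and the second is stable, their outcomes may change by different amounts with no training at all. The baseline value in the ANCOVA captures only part of this, because two patients with the same baseline MIP can be at different points of recovery. The SAP's model does not use even the baseline value.

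Two things are at stake. A mixed population adds outcome variance that a planned covariate could remove. With 22 per arm, recent patients may also fall unevenly between the arms, and the unadjusted estimate then moves by chance in either direction. A later adjustment needs the event dates, and the protocol names that date for CABG patients only.

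**Working it through.** **Inputs from the documents.** 44 patients, 22 per arm (sections 1 and 9.1); 20 per arm evaluable, a 23 cmH2O difference in MIP, 5% significance and 90% power (section 9.1).

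**Inputs assumed, because the documents give none.** The share p of patients with a recent event: 20% to 50%. The extra untreated 4-week change d in recent patients, in residual SDs: 0.5 and 1.

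**Step 1: the plan's own sample size, as a scale.** Section 9.1 states no SD, so its 20 per arm can be neither confirmed nor refuted. Solving for the SD that it implies, with a two-sided 5% level assumed:

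SD = 23 / [√(2/20) × (1.960 + 1.282)] = 23 / (0.3162 × 3.242) ≈ 22.4 cmH2O by the normal formula, or 21.9 with the t distribution. The target effect is then 23/21.9 ≈ 1.05 SD.

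**Step 2: lost precision.** Mixing two groups whose mean changes differ by d multiplies the residual variance by 1 + p(1 − p)d². The loss in patients is 44 × (1 − 1/ratio).

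| d | p | variance ratio | patients lost, of 44 |
|---|---|---|---|
| 0.5 | 0.2 | 1 + 0.16 × 0.25 = 1.040 | 1.7 |
| 0.5 | 0.3 | 1 + 0.21 × 0.25 = 1.053 | 2.2 |
| 0.5 | 0.5 | 1 + 0.25 × 0.25 = 1.063 | 2.6 |
| 1 | 0.2 | 1 + 0.16 = 1.16 | 6.1 |
| 1 | 0.3 | 1 + 0.21 = 1.21 | 7.6 |
| 1 | 0.5 | 1 + 0.25 = 1.25 | 8.8 |

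**Step 3: chance imbalance.** With 22 of 44 patients allocated to each arm and no stratification, the number of recent patients in one arm is hypergeometric.

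- 13 recent patients (30%): the probability of 9 v 4 or worse, in either direction, is 0.185.
- 22 recent patients (50%): the probability of 13 v 9 or worse is 0.366.

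**Step 4: what such a split does to the estimate.** A 9 v 4 split moves the unadjusted difference by (9 − 4)/22 × d = 0.227d. That is 0.11 SD at d = 0.5 and 0.23 SD at d = 1, against a target near 1.05 SD. If the residual SD for MIP is about 22 cmH2O, the shifts are 2.5 and 5 cmH2O against the 23 cmH2O target.

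**Step 5: which adjustment remains possible.** The diagnosis may be recoverable from the past-medical history. Time since event is secured for CABG patients only. For PCI, MI and heart failure it depends on whether the unspecified history happens to carry dates.

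**The case against.** A reader might infer that differences in natural recovery are left neither balanced nor adjustable. The documents do not support that. Randomisation balances recovery in expectation, and the significance level and confidence interval already allow for chance imbalance. Past-medical history is collected, so the diagnosis could serve as a covariate.

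A reader might also infer that only the CABG date will be recorded. The sentence in section 17.3 sits under data handling and is introduced as a list of inclusions, so it is not closed. All that can be said is that CABG is the only event whose date is named. The clearest example of a recovering patient, one shortly after surgery, is in fact the one whose date is secured. That the trial enrolled only CABG patients before Revision 1 is likewise an inference from the revision history and the remaining CABG date.

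The premise itself is not documented. Section 3 of the protocol links heart disease to lower respiratory pressures, but says nothing about the rate of recovery, its dependence on recency, or natural change in FMD or pulse wave velocity. At d = 1, recent patients would gain about 22 cmH2O more MIP than remote patients without training, close to the whole target effect, so that value is a high one for MIP. Recruitment ahead of rehabilitation may also narrow the spread of event dates in practice, although it sets no formal window.

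These objections stand. They limit the point to precision, chance imbalance and unsecured data. They do not explain why the date item covers one of four qualifying conditions, or why neither analysis uses the qualifying event.

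**Conclusion.** The point holds as a gap in data collection and analysis. The collection item in section 17.3 does not match the eligibility in section 7.1, and no planned model uses diagnosis or time since event.

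The likely cost is small to moderate. If 20-50% of patients are recent, it is worth about 2-3 of 44 patients at d = 0.5 and about 6-9 at d = 1. A split of 9 v 4 or worse has probability 0.185 when 13 are recent; at exactly 9 v 4 the unadjusted estimate shifts by 0.11 or 0.23 SD. For comparison, the allowance for losses in section 9.1 is 4 patients (44 − 40).

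All of these figures rest on assumed values of p and d. If recent and remote patients change alike over 4 weeks, the loss is nil. Baseline adjustment under the protocol ANCOVA could absorb part of the difference; the SAP's model would not. The recommendation rests mainly on its low cost and on the difficulty of recovering dates afterwards.

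**What to change.** 1. In protocol sections 11 and 17.3, replace the CABG date with the type and date of the most recent qualifying event for every patient: CABG, PCI, MI, or heart-failure diagnosis or hospitalisation.
2. In section 17.1, prespecify one binary covariate, recent versus remote qualifying event, in the baseline-adjusted ANCOVA. The sponsor fixes the cut-point, and the rule for heart-failure patients without a single dated event, before unblinding. The factor should rest on recency alone: grouping all surgical patients with recent ones would place a long-past CABG beside fresh events.
3. Align the SAP with that model in place of the analysis of variance on change.
4. Optional, and only if enrolment has not begun: generate a blocked list stratified by the same factor. If enrolment has begun, steps 1 to 3 suffice, with dates obtained for patients already enrolled.

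Cost: one form field and one degree of freedom. The optional step adds one more list to manage. No patients are added and eligibility does not change.

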### **7.2 Exclusion criteria as follows;**

- <18 years of age

**PROTOCOL TITLE:** Effects of high-intensity inspiratory muscle training as a pre-cardiac rehabilitation intervention on cardiovascular functions in patients with heart disease

- Being a current smoker (or tobacco).
- Having a diagnosed chronic disease such as inflammatory bowel disease/irritable bowel syndrome, cerebrovascular diseases, COPD, chronic kidney disease requiring dialysis, neurological disorders, or diseases that may affect motor/cognitive function [multiple sclerosis, Parkinson's disease, polio, Alzheimer's disease, dementia, or other brain diseases of ageing])
- Getting a score below 24 on the Standardized Mini Mental Test
- Using antipsychotic medications commonly used to treat schizophrenia or schizoaffective disorders (i.e., haloperidol)
- Having had any other previous thoracic operation except CABG (e.g. Pneumonectomy, lobectomy, etc.)
- Having a history of unstable-angina
- Having had pneumonia in the last 3 months

